8.2.5.2. Echocardiography/ MUGA scan

An echocardiography or a MUGA scan will be performed during the study to assess cardiac function. The same technique (either echocardiography or MUGA) should be used throughout the study for a given patient.

At inclusion visit, if LVEF is < 50%, the patient is ineligible.

During the study, the management of decrease in LVEF is based on the measured LVEF and LVEF change from baseline described in [section 8.12](#).

GLS assessment will be assessed during echocardiography, whenever possible (not mandatory), to follow left ventricular systolic dysfunction, at the time points already defined for echocardiography.

8.2.5.3. Cardiac marker follow-up

In order to monitor a potential cardiac toxicity, a cardiac marker assessment, including troponin, CPK-MB and BNP, will be performed at predose, 6h, 24h, 48 and 72h after S64315 EoI on the days of LID1 (D-13) and LID2 (D-6), C1D2 and C1D9 and at each pre-dose assessments for the following visits.

Either troponin I or T assessment can be used, but it should be ultra-sensitive, whenever possible. The same subtype (either I or T) should be used throughout the study. If, for a given centre, both troponin I and T can be assessed, priority should be given to troponin I.

In case of troponin increase observed after any of the first two S64315 infusions during cycle 1 (C1D2 or C1D9), it will be recommended to assess these cardiac markers at 48h and 72h S64315 EoI and after each subsequent S64315 infusions (before discharge and beyond, if needed) on a regular basis according to the investigator's judgment.

In case of troponin increase $> 10\times\text{UNL}$ or a troponin increase consistent with the diagnosis of a myocardial infarction (Grade 3), the patient should discontinue study treatment (see [section 8.12](#)).

8.2.5.4. MRI assessment

A cardiac MRI should be performed at the time of the event (as far as possible within 48 to 72h) in case of troponin increase $> 10\times\text{ULN}$ or in case of troponin increase $> \text{ULN}$ associated with clinical signs or LVEF decrease or ECG abnormality, to detect a potential acute structural effect related to S64315. Another cardiac MRI should be performed 5 or 6 weeks later, to detect any long-term damage related to S64315.

In case of MRI abnormality in this context of troponin increase, the patient should discontinue study treatment (see [section 8.12](#)).

8.2.5.5. 24-hour Holter assessment

A 24-hour Holter should be set-up in case of troponin increase $> 10\times\text{ULN}$ (immediately once detected) or troponin $> \text{ULN}$ associated with clinical signs or LVEF decrease or ECG abnormality to detect arrhythmia. Abnormalities considered clinically significant by the investigator and/or local cardiologist will be reported in the eCRF as adverse events.

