Creatine kinase (CK) / Creatine phosphokinase (CPK)	Grade ≥ 3 serum CK/CPK Grade 3 isolated electrolyte abnormalities (i.e. those occurring without clinical consequence) not recovered with or without intervention, to Grade < 2 level within 72 hours

TOXICITY	DLT CRITERIA
Electrolyte abnormalities (including magnesium, calcium, phosphorus, etc.) clinically significant	Any Grade 4 electrolyte abnormality
Cardiac disorders	QTcF interval \geq 501 ms or increase of $>$ 60 ms from baseline on at least two separate ECG assessments (1 assessment = triplicate ECG) Asymptomatic, absolute decrease in LVEF of 10% or greater from baseline AND LVEF $<$ 50% Asymptomatic, absolute decrease in LVEF of 20% or greater from baseline Troponin increase $>$ 10xULN or a troponin increase consistent with the diagnosis of a myocardial infarction (Grade 3) Symptomatic congestive heart failure
Skin and subcutaneous tissue disorders	Grade \geq 3 rash
Haematological abnormalities	Grade 4 neutropenia and/or thrombocytopenia persisting for 28 days after the start of azacitidine dosing in a cycle of therapy in the absence of active AML ($<$ 5% blasts) or active MDS or myelofibrosis
Other AEs	Any Grade \geq 3 AE Single event or multiple occurrences of the same event that lead to a dosing delay of $>$ 7 days in a cycle may be considered to be DLT by the Investigators and the Sponsor, even if not Grade \geq 3 Failure to restart test drug administration at the same dose due to drug-related toxicity Failure to restart test drug administration at the same dose within one cycle (i.e. 28 days) of the first missed dose due to delayed recovery from drug-related toxicity Failure to initiate cycle 1 after completing the LID period or failure to receive LID2 after receiving the LID1, due to drug-related toxicity
NCI CTCAE v5.0 will be used for grading	

The following criteria will not be considered as DLT:

- Grade 3 nausea, vomiting, diarrhoea, anorexia or constipation that do not result in hospitalization, tube-feeding or use of TPN
- Grade 3 fatigue, asthenia, fever
- Grade 3 isolated electrolyte abnormalities (i.e. those occurring without clinical consequence) that resolve, with or without intervention, to Grade $<$ 2 level in 72 hours

Patients who meet any of the criteria included in Table (4.1.3.5) 2 at the end of Cycle 1 will not be evaluable for DLT and therefore will be replaced during the dose escalation phase I part of the study, but not in the expansion parts of the study.

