8.12. Management of treatment dose adaptations due to toxicities

For patients who do not tolerate the protocol-specified dosing schedule, dose interruptions and/or reductions are either recommended or mandated in order to allow patients to continue the study treatments.

Dose modifications recommendations for S64315 are summarised in [Table \(8.12\) 1](#).

A patient must discontinue treatment with S64315 if, after treatment is resumed at a lower dose, the toxicity recurs with the same or worse severity, unless in the opinion of the investigator it is in the patient's best interest to continue S64315, and upon documented agreement with the Sponsor.

For each patient, once a dose reduction has occurred, the dose may not be re-escalated during the subsequent cycles unless in the opinion of the investigator it is in the patient's best interest to continue S64315, and upon documented agreement with the Sponsor.

When a patient meets the criteria for S64315 discontinuation described in the table, he/she must discontinue both IMPs.

Dose modifications for azacitidine must be done according to azacitidine E.U. SmPC (see [Table \(8.12\) 2](#)).

These dose changes must be recorded in the eCRF.

Table (8.12) 1 - Criteria for interruption and re-initiation of S64315

Recommended dose modifications for S64315	
Worst toxicity CTCAE Grade^a (unless otherwise specified)	During a cycle of therapy
Investigations (Renal)	
Serum creatinine	
Grade 2 (> 1.5 – 3 x ULN or > 1.5 – 3 x baseline)	Omit dose until resolved to Grade ≤ 1 or baseline, then: - If resolved in ≤ 14 days, then maintain dose level - If resolved in > 14 days, then ↓ 1 dose level
Grade 3 (> 3 – 6 x ULN or > 3 x baseline)	Omit dose until resolved to Grade ≤ 1 or baseline, then ↓ 1 dose level
Grade 4 (> 6 x ULN)	Discontinue patient from test drug treatment
Note: If intercurrent illness, e.g. dehydration due to diarrhoea or febrile infections, leads to prerenal insufficiency, this should not be considered drug related and the criterion for dose modification not fulfilled	
Investigations (Hepatic)	
Isolated Total Bilirubin elevation^b	
Grade 2 (> 1.5 - 3.0 x ULN if baseline was normal, >1.5 - 3.0 x baseline if baseline was abnormal)*	Omit dose until resolved to Grade ≤ 1, then: - If resolved in ≤ 14 days, maintain dose - If resolved in > 14 days, ↓ 1 dose level

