NOTE: Upon discontinuation due to LVEF decrease, closely monitor LVEF until resolution. The same cardiac imaging modality (i.e. transthoracic echocardiography (TTE) or MUGA scan) used at baseline is to be used for all subsequent assessments	
Cardiac MRI abnormality	In case of cardiac MRI abnormality clinically significant according to the cardiologist (e.g. compatible with ischemia or left ventricular dysfunction), in a context of troponin elevation, discontinue patient from study drug treatments
Cardiac biomarkers	
Grade 1 troponin I or T elevation	Omit dose, evaluate and treat patient per institutional guidelines. Follow Troponin I/T to resolution per institutional guidelines 
 - If no evidence of LVEF decrease from baseline of 10% or greater on TTE or MUGA* and Troponin I/T resolves to normal in \leq 7 days, then maintain dose level - If no evidence of LVEF decrease from baseline of 10% or greater on TTE or MUGA* and Troponin I/T resolves to normal in $>$ 7 days, then \downarrow 1 dose level. Consult with a cardiologist prior to re-initiating test drug - If evidence of LVEF decrease from baseline of 10% or greater on TTE or MUGA, follow guidelines for LVEF decrease

	*exams to be performed once per cycle or according to physician decision A clear investigation is required in case of isolated increase in troponin in order to consider the possible confounding factors before considering the abnormality as related to the test drug
Troponin I or T elevation > ULN associated with clinical signs or LVEF decrease or ECG abnormality	A cardiac MRI should be performed at the time of the event (as far as possible within 48h to 72h) and 5 to 6 weeks later, for functional cardiac assessment A 24-h Holter should be performed at the time of the event
Troponin I or T elevation > 10 x ULN or troponin increase consistent with the diagnosis of a myocardial infarction (Grade 3)	Discontinue the patient from test drug treatments A cardiac MRI should be performed at the time of the event (as far as possible within 48h to 72h) and 5 or 6 weeks later, for functional cardiac assessment A 24-hour Holter should be performed at the time of the event
Eye Disorders (Results and images of ophthalmic examinations should be made available upon request)	
Other ocular/visual toxicity	
Grade 1 or 2	Maintain dose level and increase ophthalmic monitoring frequency to at least every 14 days Refer the patient to an ophthalmologist within one week for evaluation

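### Section 8.2.5.4 and Table (8.12) 1 give different MRI triggers for stopping treatment after a troponin rise, and the protocol does not say which governs

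*Protocol*

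**What the plan says.** Section 8.2.5.4 orders a cardiac MRI when troponin exceeds 10 x ULN, or exceeds ULN together with clinical signs, LVEF decrease or ECG abnormality. It then gives the consequence: "In case of MRI abnormality in this context of troponin increase, the patient should discontinue study treatment", followed by a pointer to section 8.12.

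The matching row of Table (8.12) 1 begins "In case of cardiac MRI abnormality clinically significant according to the cardiologist", offers ischaemia and left ventricular dysfunction as examples, and ends "in a context of troponin elevation, discontinue patient from study drug treatments". No row covers an MRI abnormality that the cardiologist considers not significant.

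Three other rows or sentences matter:

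- The row "Troponin I or T elevation > ULN associated with clinical signs or LVEF decrease or ECG abnormality" asks for MRI and Holter but states no stop.
- For troponin above 10 x ULN or consistent with myocardial infarction, the action is "Discontinue the patient from test drug treatments". Section 8.2.5.3 says the same.
- Section 8.12 adds: "When a patient meets the criteria for S64315 discontinuation described in the table, he/she must discontinue both IMPs".

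Among the DLT criteria in Table (4.1.3.5) 1 is "Failure to restart test drug administration at the same dose due to drug-related toxicity".

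**The concern.** The two places attach permanent discontinuation to different findings. One refers to an MRI abnormality without qualification. The other refers to an abnormality that has passed a named assessor's judgement of clinical significance. A site working from 8.2.5.4 has a complete instruction and could act on it without opening the table. A site working from the table could keep the same patient on treatment.

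The consequences go beyond individual management. The SAP (4.2.1.2) has a deviation category for patients who met a withdrawal criterion but were not withdrawn, and such a patient could be coded either way. DLTs are taken from the investigator's report and not recalculated (SAP 4.2.3.1), so the analysis cannot even out differences between sites. Cardiotoxicity was the dose-limiting toxicity of S64315 as a single agent (protocol 2.2.2), so this is not a peripheral rule.

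**Working it through.** **Where the two rules diverge.** Take a patient whose MRI abnormality the cardiologist judges not clinically significant.

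| Troponin | Section 8.2.5.4 | Table (8.12) 1 | Conflict |
|---|---|---|---|
| > 10 x ULN, or consistent with myocardial infarction | stop | stop, by the troponin row | no |
| > ULN, not > 10 x ULN and not consistent with infarction, with clinical signs, LVEF decrease or ECG abnormality | stop | MRI row not met; other rows may allow resumption | yes |

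In the second line the Grade 1 troponin row decides what happens next under the table. If LVEF has not fallen by 10% or more, treatment resumes at the same dose when troponin normalises within 7 days, and one level lower when it takes longer. If LVEF has fallen by 10% or more, the LVEF rows apply.

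**Whether the difference reaches the DLT count.**

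1. Section 4.1.3.5 requires a DLT to be a clinically significant adverse event, at least possibly related to the test drug, that also meets a table criterion. An MRI finding judged not significant does not qualify alone. The accompanying troponin, ECG or clinical event would have to.
2. If the stop is not a DLT and falls before C1D28, Table (4.1.3.5) 2 makes the patient non-evaluable, and the patient is replaced.
3. A DLT at LID1 or LID2 is assigned to 25 or 50 mg monotherapy and the patient is replaced (section 10.2.6). It is not a combination-cohort result.
4. If troponin takes more than 7 days to normalise, the table itself lowers the dose, which can already meet the failure-to-restart criterion. The readings differ mainly for fast-resolving cases without an LVEF fall of 10% or more.

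**Size, if one patient is reclassified as a DLT.** Inputs are the printed priors in Appendix 8:

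- (log α1, log β1) bivariate normal, means (-0.092, -0.507), SDs (0.982, 0.694), correlation 0.705, reference dose 1400 mg
- log α2 normal, mean -3.75, SD 2, with azacitidine at its reference dose
- η normal, mean 0, SD 9.902

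The model, from section 10.2.2, is logit π1 = log α1 + β1 log(d/1400) and logit π2 = log α2. The combination odds of DLT are exp(η d/1400) x (π1 + π2 - π1π2) / ((1 - π1)(1 - π2)). With k DLTs in n patients at 50 mg, prior draws are weighted by p50^k (1 - p50)^(n - k), where p50 is the DLT probability at 50 mg. The result is the weighted share of draws with a DLT rate at 100 mg of at least 33%.

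Check against the plan: Table (1.3) 1 prints 0.0666 after 0/5 and 0.2246 after 1/5 at 50 mg. The rebuilt model gives 0.067 and 0.222.

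| Evaluable at 50 mg | 0 DLT | 1 DLT | 100 mg allowed after 1 DLT (limit 0.25) |
|---|---|---|---|
| 3 | 0.107 | 0.329 | no |
| 4 | 0.085 | 0.269 | no |
| 5 | 0.067 | 0.222 | yes |
| 6 | 0.054 | 0.184 | yes |

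**The case against.** The best defence is that the passages can be read together. Section 8.2.5.4 does not say that every abnormality counts, and it sends the reader to the section on dose adaptation. Other cardiac sections use the same pointer for QTc, LVEF and troponin. On that reading 8.2.5.4 is a summary and the table supplies the criterion and the assessor.

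Part of this stands: it is a plausible way to harmonise the texts. But no sentence says that the table prevails. In the preceding section, 8.2.5.3, the same pointer leads to a table row that agrees in substance, so a reader would expect agreement here too. The next section, 8.2.5.5, does include a clinical-significance qualifier when it says which Holter abnormalities to report as adverse events. Its absence from the MRI sentence can therefore be read as intended.

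A second objection is that the affected group is narrow. That stands in full.

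A reader might also infer that every MRI-driven stop in Cycle 1 becomes a DLT and so blocks escalation. The documents do not support that, for the four reasons listed in the working. The crossing of the 25% limit is also confined to cohorts of 3 or 4. Appendix 8's own illustration uses a first cohort of 5, where one DLT still leaves 100 mg allowed.

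**Conclusion.** The two stopping rules conflict as written for one defined group: troponin above ULN, not above 10 x ULN and not consistent with myocardial infarction, with clinical signs, LVEF decrease or ECG abnormality, and an MRI abnormality judged not clinically significant. For them 8.2.5.4 stops treatment and the table may not. Patients above the higher troponin threshold are unaffected.

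The effect on deviation coding follows directly. The effect on the DLT count is conditional: it needs a Cycle 1 stop attributed to a clinically significant drug-related event, in a patient who under the other reading would have resumed at the same dose and stayed evaluable. Given that, one reclassified patient at 50 mg changes whether 100 mg is allowed with 3 or 4 evaluable patients and not with 5 or 6. Those figures cover this one escalation step and rest on the priors printed in Appendix 8.

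How often such MRI findings occur is not given, so no expected effect on the trial can be calculated. The SAP (1.3 and 1.3.1) records that escalation was stopped and expansion will not run. What remains at stake is therefore any patient still on treatment and the consistency of DLT and deviation reporting. It should be corrected, but it does not threaten the design.

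**What to change.** Reconcile section 8.2.5.4 and Table (8.12) 1 so that both state the same MRI trigger for discontinuation and the same assessor. The sponsor decides which trigger applies; this review takes no position on that. The cost is one sentence of protocol wording.

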8.2.6. Hepatic safety

Considering the results of the GLP toxicity studies showing some hepatotoxic effect of the drug, the hepatic safety will be closely monitored. An increase in serum liver enzymes should be followed by repeated testing including all the usual serum measures (at least ALT, AST, ALP and total bilirubin) to confirm the abnormalities and to determine if they are increasing or decreasing as follows:

- For isolated Grade 3 total bilirubin increase ($> 3\times\text{ULN}$) or isolated Grade 3 AST or ALT increase ($> 5\times\text{ULN}$), the patient should be weekly monitored, including LFT: albumin, ALT, AST, total bilirubin, fractionated if total bilirubin $> 2.0\times\text{ULN}$, ALP, fractionated if ALP $> 2.0\times\text{ULN}$, and GGT, or more frequently if clinically indicated, until values have resolved to baseline or stabilised over 4 weeks
- For AST or ALT $> 3.0\times\text{ULN}$ combined with total bilirubin $> 2.0\times\text{ULN}$, repeat LFT as soon as possible, preferably within 48h from awareness of the abnormal results, then with weekly monitoring of LFT, or more frequently if clinically indicated, until AST, ALT, or bilirubin values have resolved to baseline or stabilised over 4 weeks

Clinically significant abnormalities should be carefully documented in the patient's medical file.

Additional tests to evaluate liver function such as INR (or biopsy if appropriate) may be performed as appropriate. Close observation and documentation also include:

- obtaining a more detailed history of symptoms and prior or concurrent diseases, obtaining a history of concomitant drug use (including non-prescription and herbal and dietary supplement preparations), alcohol use
- performing liver imaging (ultrasound, magnetic resonance or computerized tomography) to evaluate biliary tract or liver disease
- ruling out acute viral hepatitis types A, B, C, D, and E; autoimmune or alcoholic hepatitis; hypoxic/ischemic hepatopathy; NASH; and biliary tract disease
- considering gastroenterology or hepatologist consultations

The recommendations towards the study according to the level and evolution of hepatic abnormalities are detailed in [section 8.12](#).

8.2.7. Monitoring of infections that may occur with neutropenia

A possible co-toxicity on bone marrow and lymphoid organs, identified as primary target organs for both compounds in the toxicology studies, should be considered. Therefore, WBC count should be closely monitored, and caution should be exercised in assessing the possibility of infections in the patients receiving S64315 in combination with azacitidine.

Early initiation of empirical broad-spectrum antibacterial antibiotics is recommended in the event of fever. If fever persists for 4 to 7 days, an antifungal treatment should also be considered. Investigators should employ these agents in compliance with best medical practices and institutional guidelines and standards. Before initiating these treatments, the list of non-authorized treatments must be consulted. For quinolone agents, besides the possible DDI, the possible risk of prolongation of the QTc interval must be assessed (refer to [section 6.3](#) and 'Guidance on use of co-medication for CL1-64315-004 clinical study').

The use of recombinant hemopoietic growth factors, specifically prohibited in Cycle 1, may be used beyond Cycle 1 at the discretion of the Investigator.

8.2.8. Gastrointestinal disorders

8.2.8.1. Nausea and vomiting management

Considering the GLP toxicity studies and the preliminary clinical data with S64315 (as of September 5, 2019, 23 (60.5%) and 19 (50%) out of 38 patients treated in the S64315 single agent AML and MDS study experienced nausea and vomiting respectively), nausea/vomiting prophylaxis is strongly recommended before each S64315 infusion.

Dexamethasone administration is mandatory at least 1h before S64315 infusion on the days of L1D1 and L1D2, and on C1D2.

Based on international guideline ([ASCO, 2011](#)), this prophylaxis consists in a two-drug combination of palonosetron and dexamethasone, before each S64315 infusion, followed by dexamethasone maintenance for two days after each S64315 infusion.

According to azacitidine E.U. SmPC, patients should be premedicated with anti-emetics for nausea and vomiting.

The recommended prophylaxis is displayed in the [Table \(8.2.8.1\) 1](#).

Table (8.2.8.1) 1 - Treatments schedule for nausea/vomiting prophylaxis

LID1 and LID2	Palonosetron 0.25 mg IV or 0.5 mg p.o.+ Dexamethasone 8 mg p.o. / IV 1h before each S64315 infusion, followed by dexamethasone 8 mg p.o. / IV during two days after each S64315 infusion, as required
CxD ₁	Metoclopramide IV before azacitidine administration
CxD ₂	Palonosetron 0.25 mg IV or 0.5 mg per os (p.o.) before azacitidine administration + Dexamethasone 8 mg p.o. / IV. 1h before S64315 infusion
CxD ₃	Dexamethasone 8 mg p.o. / IV. as required
CxD ₄	Dexamethasone 8 mg p.o. / IV. as required
CxD ₉	Palonosetron 0.25 mg IV or 0.5 mg p.o.+ Dexamethasone 8 mg p.o. / IV before each
CxD ₁₆	S64315 infusion, followed by dexamethasone 8 mg p.o. / IV during two days after each
CxD ₂₃	S64315 infusion, as required

If palonosetron is not available, clinicians may substitute with a first-generation 5-HT₃ serotonin receptor antagonist (i.e. granisetron/ dolasetron/ tropisetron, to be used with caution according to ‘Guidance on use of co-medication for CL1-64315-004 clinical study’).

Limited evidence also supports adding aprepitant to the combination, if the above combination does not provide sufficient nausea/vomiting control.

As a reminder, ondansetron is prohibited along the study due to the risk of QTcF prolongation (see ‘Guidance on use of co-medication for CL1-64315-004 clinical study’).

For patients who experience nausea and/or vomiting despite optimal prophylaxis, clinicians should re-evaluate emetic risk, disease status, concurrent illnesses, and medications and consider adding lorazepam or alprazolam or adding a dopamine antagonist to the regimen.

Please refer to [sections 6.3.1](#) and [6.3.2](#) for more information about the prohibited medications and the medications to be used with caution during IMP treatment.

